6.4. STATISTICAL TESTS

The default significant level will be 5%; confidence intervals will be 95% and all tests will be two-sided, unless otherwise specified in the description of the analyses.

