6.5. COMMON CALCULATIONS

The statistical analysis of the data obtained from this study will be performed using SAS® version 9.4 or higher.

Unless otherwise specified, descriptive statistics for continuous variables will be presented using the number of non-missing observations, mean, standard deviation, median, minimum and maximum. In general, the same number of decimal places as in the raw data will be presented when reporting minimum and maximum, one more decimal place than in the raw data will be presented when reporting mean and median, and two more decimal places than in the raw data will be presented when reporting standard deviations. If the raw data have three or more decimals, three decimals will be presented for mean, median, minimum and maximum, and standard deviation.

For categorical endpoints, descriptive statistics will be presented using the frequency counts and percentage of subjects in the various categories of the variable. All percentages will be presented with one decimal, except percentages less than one, which should be presented with 2 decimals or more, as appropriate.

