In In addition, a sensitivity (secondary) analysis for the primary effectiveness endpoint will be performed to evaluate the comparability across the 2 strata by using a logistic regression model, with success/failure for primary endpoint as dependent variable and with stratification factor (mild/moderate), treatment group and interaction between stratification factor and treatment group as independent variables included in the model.

An example of SAS code is provided below:

proc logistic data=primaryend;

class treatment success;

model success= treatment strata treatment*strata / expb;

run;

It is not anticipated that there will be data missing for the primary or secondary effectiveness endpoints, but, if these is, the analyses based on the ITT set will consider missing data as failures for these endpoints.

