13.2.1. ANALYSIS OF SECONDARY EFFICACY VARIABLES

The secondary effectiveness endpoints will be summarized descriptively by treatment group and overall, using frequency counts and associated percentages, for the ITT analysis set.

For the binary (success/failure) secondary effectiveness endpoints (3 and 10 minutes hemostasis endpoints), within-treatment group two-sided 95% confidence intervals will be reported for the proportion of successes using the Clopper-Pearson method. A two-sided 95% confidence interval for the difference in proportion of successes between treatment groups (Test minus Control) will also be calculated for each binary secondary effectiveness endpoint using the FM score method; however, no testing for non-inferiority will be carried out.

In addition, within each TBS bleeding severity level (Mild, Moderate), the binary secondary effectiveness endpoints will be summarized descriptively by treatment group and overall, using frequency counts and associated percentages.TO consult Farrington-Manning (FM) 1 method to calculate the percentage difference and the confidence interval through the following procedure: proc freq data=raw1;

tables trt*ae1or0 / riskdiff(cl=FM) nopercent nocol; run:

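### The example PROC LOGISTIC code in SAP 13.1.1 does not match the model described in the text: as written it either stops or prints treatment and interaction values that are not odds ratios.

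*SAP*

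**What the plan says.** SAP 13.1.1 states that "a sensitivity (secondary) analysis for the primary effectiveness endpoint will be performed to evaluate the comparability across the 2 strata by using a logistic regression". The response is success or failure on the primary endpoint, "with stratification factor (mild/moderate), treatment group and interaction between stratification factor and treatment group as independent variables included in the model". The section then says "An example of SAS code is provided below" and gives a CLASS statement, "class treatment success", and a MODEL statement, "model success= treatment strata treatment*strata / expb". There is no EVENT=, PARAM= or REF= option and no ODDSRATIO, LSMEANS or CONTRAST statement.

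The analysis "will be performed using SAS® version 9.4 or higher" (SAP 6.5). SAP 6.4 adds: "The default significant level will be 5%; confidence intervals will be 95% and all tests will be two-sided", unless otherwise specified. The interaction test therefore runs at 5% two-sided. The SAP does not state how success, treatment or strata are coded.

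SAP 13.2.1 gives one PROC FREQ call for the Farrington-Manning limits of the secondary endpoints: "tables trt*ae1or0 / riskdiff(cl=FM) nopercent nocol". The text there describes the result as the difference in proportions of successes, Test minus Control.

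**The concern.** The text treats severity as a two-level factor, but the code does not declare it as one. The code also leaves the modelled event, the parameterization and the reference levels to software defaults, and EXPB is the only effect-size output it requests.

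This is the only modelled sensitivity analysis of the primary endpoint and the only formal comparison of the treatment effect between the two severity strata. In about 210 subjects a non-significant interaction does not show that the strata are alike, so readers will look at the effect sizes. For treatment and interaction, those are the values that come out on the wrong scale, and possibly in the wrong direction.

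**Working it through.** **Inputs.** Success rates 0.85 (Powder) and 0.80 (Original), margin 0.10, 105 evaluable per arm (SAP 13.1.1). SAS 9.4 or higher (SAP 6.5). The SAS defaults used below are software knowledge, not document content, and SAS was not run; the coding was emulated with binomial logistic fits. Rates and counts by stratum are assumptions, since the documents give none for this trial.

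**The plan's own figure.** The SAP gives no number for the logistic model. Its sample size does reproduce. With rates constrained to the null (0.860 and 0.760), n = [1.96 × √(0.860×0.140 + 0.760×0.240) + 0.842 × √(0.80×0.20 + 0.85×0.15)]² / 0.15² = 104.1, so 105 per arm; power at 105 is 80.3%.

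**What the code fits.** SAS codes a two-level CLASS variable +1 (first level) and −1 (last level) by default. With T = ±1 and severity S numeric, the model is logit = a + bT + cS + dTS. The log odds ratio between arms at severity S is 2b + 2dS. It follows that:
- exp(b) is the square root of the odds ratio at S = 0;
- exp(d) is the square root of the ratio of odds ratios per unit of S;
- exp(c) is the full-scale severity odds ratio, as a geometric mean over the arms.

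If S is a character variable outside CLASS, the procedure stops.

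**Case 1: 85% v 80% in both strata.** The odds ratio for success is (0.85/0.15)/(0.80/0.20) = 1.417. The code prints √1.417 = 1.190 or 1/1.190 = 0.840.
- By default the lowest ordered response level is modelled: failure for 0/1 coding with 1 = success, but success for 1 = success, 2 = failure.
- With failure modelled and arms sorted as Original/Powder or Control/Test, the two reversals cancel and 1.190 points correctly to Powder.
- With failure modelled and Powder first, it prints 0.840, which looks adverse if read as an odds ratio for success.

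**Case 2: effect differs by stratum (assumed rates).** Mild 95% v 90%: odds ratio 19/9 = 2.111. Moderate 70% v 75%: (0.70/0.30)/(0.75/0.25) = 0.778. Ratio 0.778/2.111 = 0.368.

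| Quantity | True value | Printed with S = 1/2, failure modelled |
|---|---|---|
| Treatment | 2.11 (mild), 0.78 (moderate) | 2.39 (Original first) or 0.42 (Powder first) |
| Interaction | 0.368 | 0.61 (Original first) or 1.65 (Powder first) |

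The treatment value is √(2.111²/0.778) = 2.394 or its inverse, 0.418: an extrapolation to S = 0 that describes neither stratum. The interaction value is √0.368 = 0.607 or its inverse, 1.648.

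**What survives.** Take assumed counts of 44/50 v 46/50 (mild) and 45/55 v 38/55 (moderate), Powder v Original. The odds ratios are 0.638 and 2.013, ratio 3.157. The standard error of the log ratio is √(1/44 + 1/6 + 1/46 + 1/4 + 1/45 + 1/10 + 1/38 + 1/17) = 0.818, so z = ln(3.157)/0.818 = 1.406 and p = 0.1597. This p-value is identical for either event, either arm order, and severity coded 0/1, 1/2 or in CLASS. The strata coefficient is also full-scale: the moderate-to-mild odds ratios for success are 0.614 (Powder) and 0.194 (Original), and √(0.614 × 0.194) = 0.345 is what the code gives for success, or its inverse for failure.

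**The PROC FREQ call.** By default the limits are for column 1, first row minus second. With 0 = failure in column 1:
- Control in row 1: (1 − P_C) − (1 − P_T) = P_T − P_C, which is what the text states.
- Test in row 1: (1 − P_T) − (1 − P_C) = P_C − P_T, which is reversed. For 89/105 v 84/105, the score interval for success is (−5.7, +15.2) points and the reversed one is (−15.2, +5.7).

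**The case against.** The code is labelled an example for a secondary analysis, and the text above it specifies the model clearly. A character severity variable produces an error that would be noticed and repaired, not a wrong result. The stated purpose is comparability across strata; the interaction test answers that, and its p-value does not change whenever the code runs with a numeric two-level variable. Success counts and percentages by arm within mild and moderate are planned separately. All of this stands, and it limits the point to the printed effect sizes. It does not remove the point: the text names no reference level and asks for no stratum-specific effect, so the code alone defines that output.

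A reader might infer that every effect size printed is wrong, or that the code necessarily models failure and reverses the direction. The documents do not support that. The strata coefficient is full-scale, and event and direction depend on coding that the SAP does not state; with alphabetical arm labels and 0/1 response coding the direction is right.

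A reader might also infer that the non-inferiority verdict could flip through the PROC FREQ call. That needs two conditions the documents do not set: reuse of the call for the −0.1 rule, and Test in the first row with failure in column 1. The call sits under secondary endpoints, where non-inferiority testing is expressly ruled out. SAP 13.1.1 defines the primary interval as P_T − P_C in successes, so a reversed interval would contradict the SAP's own text.

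**Conclusion.** The point holds for the example code, and correcting it is worthwhile. Under SAS defaults the code either stops or prints treatment and interaction values that are square roots of the intended quantities: 1.19 or 0.84 against an odds ratio of 1.42 at the planning rates. With severity coded 1/2 and a real interaction, the treatment value belongs to no actual stratum.

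The interaction p-value (severity numeric), the Farrington-Manning decision rule, the sample size and the descriptive results by stratum are unaffected. The PROC FREQ example is a matter of unfixed variable, row and column, not a demonstrated error in the primary conclusion.

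The conclusion rests on known SAS defaults, which were emulated rather than run, and on assumed stratum rates and codings. The square-root relation itself does not depend on the assumed rates.

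**What to change.** In SAP 13.1.1 replace the CLASS and MODEL statements with:

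`class treatment(ref='Control') strata(ref='Mild') / param=ref;`
`model success(event='1') = treatment strata treatment*strata;`
`oddsratio treatment / at(strata=all);`

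Adapt the quoted levels to the analysis dataset and state its coding in the SAP. Adding strata to CLASS without PARAM=REF is not enough. With both factors coded ±1, the log odds ratios are 2b + 2d and 2b − 2d, which differ by 4d, so the exponentiated interaction becomes a fourth root. Firth estimation is optional and not part of this correction.

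In SAP 13.2.1 replace `ae1or0` with the hemostasis success variable, order the rows Test then Control, and set COLUMN= to the success column (COLUMN=2 when success is 1 and failure 0). The call then yields the Test minus Control difference in successes that the text describes.

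The cost is a few lines of SAP code, with no new data or subjects.

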13.2. SECONDARY EFFECTIVENESS ENDPOINT

The following secondary efficacy endpoints are included:

- Proportion of subjects achieving hemostatic success at 3 minutes following the application of SURGICEL Powder or SURGICEL Original with no re-bleeding requiring additional treatment at the TBS any time prior to initiation of final fascial closure;
- Proportion of subjects achieving hemostatic success at 10 minutes following the application of SURGICEL Powder or SURGICEL Original with no re-bleeding requiring additional treatment at the TBS any time prior to initiation of final fascial closure.

13.2.1. ANALYSIS OF SECONDARY EFFICACY VARIABLES

The secondary effectiveness endpoints will be summarized descriptively by treatment group and overall, using frequency counts and associated percentages, for the ITT analysis set.

For the binary (success/failure) secondary effectiveness endpoints (3 and 10 minutes hemostasis endpoints), within-treatment group two-sided 95% confidence intervals will be reported for the proportion of successes using the Clopper-Pearson method. A two-sided 95% confidence interval for the difference in proportion of successes between treatment groups (Test minus Control) will also be calculated for each binary secondary effectiveness endpoint using the FM score method; however, no testing for non-inferiority will be carried out.

In addition, within each TBS bleeding severity level (Mild, Moderate), the binary secondary effectiveness endpoints will be summarized descriptively by treatment group and overall, using frequency counts and associated percentages.TO consult Farrington-Manning (FM) 1 method to calculate the percentage difference and the confidence interval through the following procedure: proc freq data=raw1;

tables trt*ae1or0 / riskdiff(cl=FM) nopercent nocol; run:

14. SAFETY OUTCOMES

14.1. . SAFETY ENDPOINTS

The following safety endpoints will be included in this study:

- Incidence of thromboembolic events that were assessed as possibly related, probably related, or related to the study treatment (from enrollment through the 30-day follow-up phone call or office visit):
- Incidence of post-operative re-bleeding that was assessed as possibly related, probably related, or related to the study treatment and requiring medical/surgical intervention (from initiation of final fascial closure through the 30-day follow-up phone call or office visit);
- Incidence of SAEs requiring surgical intervention and assessed as possibly related, probably related, or related to the study treatment (from enrollment through the 6-month follow-up phone call or office visit).

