overall. The continuous data will be summarized by number of subjects, mean, standard deviation (SD), median, minimum and maximum. The categorical data will be summarized by frequency counts along with associated percentages. There are no plans for interim analyses whose intent would be to stop the study early or to adapt the study design or planned number of patients. There will be two planned analysis time points during the study. The first analysis will occur after all subjects complete phone call or office visit 1 [30 days (+ 14 days) post-surgery]. All data collected through 30-day (+14 days) follow-up will be analyzed. The second analysis will occur after all subjects complete phone call or office visit 2 [6-month (+/-30 days) post-surgery] and the data collected at this follow-up is available. The second analysis will be performed on the data from the 6-month follow-up assessing any occurrences of SAEs requiring surgical intervention and Interim assessed as possibly related or related to the randomized study Analysis treatment. The clinical study report (CSR) will be submitted to investigative sites and CFDA after the first analysis is completed. The CSR will include all primary and secondary endpoints as well as safety endpoints and data through the 30-day follow-up. An addendum to the CSR will be generated and ready for submission after the second analysis is complete, which will include data from the 6-month follow-up assessing any occurrences of SAEs requiring surgical intervention and assessed as possibly related or related to the randomized study treatment.

Confidential Page 17 of 86

Table 1: Schedule of Activities

Procedures	Screening within 21 days	Baseline within 24 hours prior	Surgical procedure	Post-surgery to hospital	30-Day F/U call or visit	6-Month F/U call or visit
Inclusion/exclusion	of procedure ¹	to procedure X	X	discharge	(+14 days)	(±30 days)
Informed consent	X	Λ	Λ			
Demographics	X					
Medical/surgical history	X	X ³				
Concomitant medications	71	X	X	X	X	
Physical exam (Vitals: BT, BP, HR, RR)	X			X^7		
CBC with Hgb	X^2			X		
Coagulation tests (PT, APTT, INR)		X ⁴				
Pregnancy test (if applicable)		X^4				
Randomization/treatment application			X			
Assessment & determination of hemostasis at TBS			X			
Operative/surgical information			X ⁵			
Assessment of bleeding			X			
Surgeon Ease of Use Survey			X^6			
Adverse events			X	X	X	
Thromboembolic events possibly related or related to the TBS			X	X	X	

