10.1.6. Criteria of Sponsor's Discontinuation of the Trial

Both the Investigator and Ethicon reserve the right to terminate the study at any time. Should this be necessary, the procedures will be arranged on an individual study basis after review and consultation with both parties. In terminating the study, Sponsor and the Investigator will ensure that adequate consideration is given to the protection of the subjects' interests and safety.

The Sponsor has the right to terminate the study early for a single site, multiple sites or all sites temporarily or permanently. Reasons may include, but are not limited to: safety issue or ethical issue, inaccurate or incomplete data record, non-compliance or dissatisfactory quality or quantity of the recruited subjects. Health authorities also have the right to terminate a study.

Confidential Page 45 of 86

The Sponsor's Medical Director (Study Medical Monitor/Safety Lead) will assess all SAES for causality and expectedness and will utilize Ethicon's Product Safety Committee (PSC) to review and adjudicate the following safety signals:

- Thromboembolic events
- Postoperative re-bleeding
- Reoperations for complications assessed as possibly related or related to the study treatment.

The PSC will also review cumulative safety data from the study. The PSC will advise on the continuing safety of study subjects and those yet to be recruited to the study. Based on cumulative data from the study, the PSC may recommend whether to continue, suspend, modify, or stop the study. At the conclusion of the study, the PSC will also give a final assessment of the safety of the product from this study. The composition, responsibilities, frequency of PSC meetings, handling of emergency situations, and documentation of PSC meetings will be specified in the Safety Management Plan (SMP).

Stopping Rules:

The rules outlined below will be used to determine if the clinical trial should be put on hold, contingent on PSC recommendations:

- If three confirmed thromboembolic SAEs (pulmonary embolism [PE] / deep vein thrombosis [DVT]) are reported and assessed as being related to SURGICEL Powder
- If one or more subjects develop post-operative bleeding and the TBS is confirmed as the cause of the re-bleeding. The relatedness of the SAE to SURGICEL Powder is to be determined by the following:
 - o Findings at re-operation
 - o Findings of TBS re-bleeding at autopsy (if applicable).

Flow of Sponsor's Discontinuation of the Trial:

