- Incidence of thromboembolic events that were assessed as possibly related or related to the study treatment (from enrollment through the 30-day follow-up phone call or office visit);
- Incidence of post-operative re-bleeding that was assessed as possibly related or related to the TBS and requiring medical/surgical intervention (from initiation of final fascial closure through the 30-day follow-up phone call or office visit);
- Incidence of SAEs requiring surgical intervention and assessed as possibly related or related to the study treatment (from enrollment through the 6-month follow-up phone call or office visit)

The incidence of adverse events (AEs) will be assessed at the preferred term level using the Medical Dictionary for Regulatory Activities (MedDRA) for event categorization. Incidence of AEs will also be assessed by onset time (intraoperative or postoperative), relationship to study surgical procedure, relationship to the study product, severity, and seriousness.

All continuous variables will be summarized by number of subjects, mean, standard deviation, median, minimum and maximum. All categorical data will be summarized by frequencies and associated percentages. No inferential statistics will be generated for

Confidential Page 65 of 86

secondary efficacy and safety endpoints.

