14.7. CHANGES FROM THE PROTOCOL SPECIFIED ANALYSIS

-For clarity, "relationship to TBS" was changed to "relationship to study treatment" in the definition of the following safety endpoint: "Incidence of post-operative re-bleeding that was assessed as possibly related, probably related, or related to the study treatment and requiring medical/surgical intervention (from initiation of final fascial closure through the 30-day follow-up phone call or office visit)".

-The text defining the PP set and major protocol deviations was changed from:

"Per-Protocol (PP) analysis set (set of evaluable subjects) consists of all ITT subjects who have no major protocol deviations and have data available for primary effectiveness endpoint. Subjects will be classified according to randomized treatment. Major protocol deviations are deviations that have an impact on the primary effectiveness endpoint. These will be determined prior to database lock."

to:

"Per-Protocol (PP) analysis set (set of evaluable subjects) consists of all ITT subjects who have no major protocol deviations affecting the primary effectiveness endpoint and have data available for this endpoint. Subjects will be classified according to randomized treatment. Major protocol deviations will be determined prior to database lock."

This change is required to maintain consistency with the manner in which the assessment of the major protocol deviations was performed for this study - major deviations that do not affect the primary effectiveness endpoint did not exclude subjects from the PP set.

The text defining the SS set was changed from:

"Safety analysis set consists of all subjects who received study product. Subjects will be classified according to treatment received."

to:

"Safety analysis set consists of all subjects who received study product. Subjects will be classified according to actual treatment received and at least post-baseline follow up"

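### SAP 14.1 counts post-operative re-bleeding by relation to the study treatment, not to the TBS as the protocol does; the only reason given is clarity, and the SAP text plans no by-arm TBS-related count

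*SAP*

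**What the plan says.** The protocol gives the re-bleeding endpoint in the Synopsis and in Sections 10.1.4, 10.1.13 and 13.2. In each place it is tied to the bleeding site: "Incidence of post-operative re-bleeding that was assessed as possibly related or related to the TBS and requiring medical/surgical intervention". The window runs from the start of final fascial closure to the 30-day follow-up.

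The other two safety endpoints in the same lists are tied to the product. The thromboembolic endpoint, for example, reads "Incidence of thromboembolic events that were assessed as possibly related or related to the study treatment".

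The SAP states that it is based on protocol version 1.1. Its Section 14.1 keeps the window and the intervention requirement but changes the attribution: "Incidence of post-operative re-bleeding that was assessed as possibly related, probably related, or related to the study treatment and requiring medical/surgical intervention". Section 14.7 reports that relationship to the TBS became relationship to study treatment "in the definition of the following safety endpoint". The only reason it offers is clarity.

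**The concern.** Where a re-bleed came from and whether the product caused it are different questions on their face. A hemostat can fail to hold at the site where it was applied, and the investigator may still attribute the re-bleed to the operation or to the patient. Under the protocol wording that subject counts. Under the SAP wording the subject does not, unless the event is also rated at least possibly related to the study treatment.

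This is a pre-specified safety endpoint in a registration trial of a hemostat. As the SAP is written, the figure reported under the endpoint's name is not the figure that the protocol defines, and a reader told that the change is for clarity would not expect the set of counted events to differ. The protocol-defined count is not shown beside it.

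**Working it through.** The plan states no figure on this point, so the check is mainly a comparison of texts.

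**1. Which events count under each definition.** All events below are post-operative re-bleeds that need intervention, within the same window.

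| Related to TBS | Related to study treatment | Protocol endpoint | SAP 14.1 endpoint |
|---|---|---|---|
| Yes | Yes | Counted | Counted |
| Yes | No | Counted | Not counted |
| No | Yes | Not counted | Counted |
| No | No | Not counted | Not counted |

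The definitions differ in the two middle rows. The second row is the practical one. The third is largely theoretical: the randomized product is applied to the TBS (Protocol 11.3.6), and other bleeding sites are treated under the institution's standard of care (Protocol Synopsis, Procedure Description).

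**2. Whether another planned output supplies the protocol count.**
- SAP 14.1.1 summarizes by arm, and within each bleeding-severity level, the endpoints as 14.1 lists them. It therefore carries the treatment-related definition.
- SAP 14.1.1 and 14.2 also tabulate adverse events by system organ class and preferred term, severity, seriousness, and relationship to the surgical procedure and to the product. None of these uses TBS attribution or combines it with the intervention requirement.
- The by-subject listings in SAP 14.2 keep the events visible, but the SAP text does not say that they show TBS attribution.

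The SAP text thus plans no by-arm count of TBS-related re-bleeding. The output templates mentioned in SAP 8 are not in the documents, so this statement covers the SAP text only.

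**3. The relatedness levels.** The protocol endpoint names possibly related and related. Protocol 19.5 has a five-level scale that includes a probable category. SAP 14.1 adds probably related, which fits that scale. The 14.7 entry shows the added level in the new wording but does not name it as a change.

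**4. Size per reclassified subject.** The Safety set size is not given. As an assumed range, take the randomized and evaluable numbers per arm in Protocol 13.3.1, 117 and 105:
- 1/117 = 0.0085, or 0.85 percentage points.
- 1/105 = 0.0095, or 0.95 percentage points.

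The documents do not allow an estimate of how many subjects would be reclassified.

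**5. Whether the TBS attribution is available.** Protocol Table 1 schedules an item for post-operative re-bleeding related to the TBS, from surgery to discharge and at 30 days. Against this, Protocol 19.5 and 19.6 describe ratings against device or treatment and procedure only, and Sections 11.5 and 11.6 ask for bleeding complications without naming the TBS. Availability has to be confirmed.

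**The case against.** The strongest reply is that the protocol does not keep the two labels apart. Table 1 lists "Thromboembolic events possibly related or related to the TBS", while the endpoint lists tie the same events to the study treatment. Since Sections 19.5 and 19.6 describe no TBS rating, moving the endpoint onto the relationship that investigators are told to record could fairly be called a clarification. The change is also disclosed with both attributions named, and Protocol 13.9 allows changes through the SAP. Little information is lost, because all events remain in the tables and listings.

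Much of this stands. The change is open and went by a permitted route. The overlap in labels is real, and the lack of a described TBS rating may be the true reason. But that reason is not the one stated, and loose wording in a schedule does not outweigh four consistent endpoint definitions. Nor can the protocol count be rebuilt from the planned tables.

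Two stronger readings are tempting and should not be drawn.

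- A reader might take the stopping rule in Protocol 10.1.6 as proof that the attributions are separate. It says "If one or more subjects develop post-operative bleeding and the TBS is confirmed as the cause of the re-bleeding" and then "The relatedness of the SAE to SURGICEL Powder is to be determined by the following". The criteria that follow are re-operation findings and TBS re-bleeding at autopsy. Evidence about the TBS is thus used to decide relatedness to Powder, and the rule links the two attributions as much as it separates them.
- A reader might infer that the definition was changed after the data had been seen, because SAP 14.7 refers in the past tense to "the manner in which the assessment of the major protocol deviations was performed for this study". That sentence belongs to the per-protocol set entry, not the re-bleeding entry. The SAP's front pages are not in the reviewed text, so missing dates cannot be held against it. Nothing shows that re-bleeding attributions were known.

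**Conclusion.** The point holds as a definition change that is disclosed but not adequately explained, with the protocol-defined count absent from the SAP text. It should be corrected, but its reach is limited. The endpoint is descriptive, so non-inferiority testing, type I error and power are untouched. The main effect is that TBS re-bleeds needing intervention but rated unlikely or not related to the product drop out.

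Each such subject lowers an arm's reported rate by 0.85 to 0.95 percentage points, on the assumption of 117 to 105 subjects per arm in the Safety set. The number of such subjects is unknown, and so is any effect on the difference between arms. The conclusion rests on the SAP text without its templates.

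**What to change.** In SAP 14.1, report two counts by arm:
1. The protocol-defined count: post-operative re-bleeding related to the TBS and needing medical or surgical intervention, with probably related added to match the five-level scale in Protocol 19.5.
2. The treatment-related count now in 14.1.

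Name the source of the TBS attribution: the re-bleeding item scheduled in Protocol Table 1 or, if it records the bleeding site, the Product Safety Committee's adjudication of post-operative re-bleeding (Protocol 10.1.6).

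In SAP 14.7, call the entry a definition change, list the added relatedness level as a change, and give the actual reason. If the reason is that no TBS attribution was recorded, say so. Detail the impact in the clinical study report, as Protocol 13.9 requires.

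The cost is one extra row, repeated within each severity level because 14.1.1 summarizes whatever 14.1 lists, plus revised wording in two sections. If TBS attribution was not recorded anywhere, the first count cannot be produced. The fix then reduces to the explanation in 14.7 and the impact statement in the report.
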